## **9. RISK OF RIVAROXABAN**

### **Potential Discomforts, Side Effects, and Risks Associated with Rivaroxaban**

The following terms are used to describe how often side effects have been seen in patients:

- Very common: it affects 1 in 10 or more subjects (10% or more)
- Common: it affects between 1 and 10 in 100 subjects (between 1% and 10%)
- Uncommon: affects between 1 and 10 in 1,000 subjects (between 0.1% and 1%)
- Rare: it affects between 1 and 10 in 10,000 subjects (less than 0.1%)

**COMMON: Seen in 1% (1 in 100 people) to 10% (1 in 10 people)**

- Internal bleedings which may occur in stomach and intestines may result in a low blood count (anemia) or decrease in blood pressure (hypotension). Other common bleeding sites include eye bleeds, bleeding from gums, nose bleeds, dark urine, heavy menstrual bleedings, hematomas (collection of blood) on the skin and small bleeds under the skin, coughing up blood, bleedings from wounds and after surgical procedures.
- Abdominal and stomach pains
- Upset stomach
- Nausea
- Constipation
- Diarrhea
- Vomiting
- Fever
- Swelling (edema; swelling caused by a fluid build-up in the body)
- Decreased general strength and energy
- Bruises
- Some enzyme levels in blood may increase (such as liver enzymes called transaminases)
- Pain in limbs (arm or leg pain)
- Dizziness (feeling dizzy)
- Headache
- Kidney problems\*
- Itching
- Rash (skin rash)

**UNCOMMON: Seen in 0.1 % (1 in 1,000 people) to 1% (1 in 100 people):**

- Increased platelet count (increased number of platelets in your blood)
- Increase heart rate
- Dry mouth
- Feeling unwell
- Allergic reactions and skin allergic reactions, like swelling of your face, skin or your limbs (angioedema, allergic edema)
- Wound oozing

- Some enzyme levels in blood may increase (i.e. lipase, amylase, alkaline phosphatase, lactate dehydrogenase, gamma-glutamyl transpeptidase and bilirubin)
- Bleeding into your joints (Intraarticular bleeding or Hemarthrosis)
- Brain bleeding or intracranial bleeding (especially in patients with high blood pressure and the elderly)
- Fainting (syncope)
- Hives (urticaria)

RARE: Seen in less than 0.1% (less than 1 in 1,000 people):

- Localized swelling
- Yellow skin (jaundice; liver problems that causes yellowing of the skin or eyes)
- Blood collection outside an arterial wall (vascular pseudoaneurysm)
- Elevation of bilirubin in the blood (break down blood product), with or without an elevation of a liver enzyme called alanine aminotransferase
- Hematomas (collection of blood) or bleeds in the muscle tissue

\*this was observed after major orthopedic surgery of the lower limbs

## 10. ADVERSE EVENT REPORTING

### I. Definitions

#### a. Adverse Event (AE)

An adverse event is any untoward medical occurrence in a clinical study subject administered a medicinal (investigational or non-investigational) product. An adverse event does not necessarily have a causal relationship with the treatment. An adverse event can therefore be any unfavorable and unintended sign (including an abnormal finding), symptom, or disease temporally associated with the use of a medicinal (investigational or non- investigational) product, whether or not related to that medicinal (investigational or non-investigational) product. (Definition per International Conference on Harmonisation [ICH]).

This includes any occurrence that is new in onset or aggravated in severity or frequency from the baseline condition, or abnormal results of diagnostic procedures, including laboratory test abnormalities.

#### b. Adverse Events of Special Interest

Events that Janssen Scientific Affairs is actively monitoring as a result of a previously identified signal (even if non-serious).

The following are considered as events of special interest, and should be reported as a serious AE:

- Suspected severe toxic effect on the bone marrow, such as severe thrombocytopenia (platelet count less than 50,000/ $\mu$ L), severe neutropenia (white blood cell count less than 500/ $\mu$ L), pancytopenia, aplastic anemia
- Suspected severe hypersensitivity reaction (eg, anaphylaxis, angioedema, severe urticaria, bronchospasm, etc.)
- Severe skin reactions such as Stevens-Johnson Syndrome
- Suspected severe liver injury

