### B. Laboratory Measurements (0 , 6 and 12 months)

All participants will be instructed to abstain from smoking, alcohol, and food intake, eg, overnight fasting or at least 10 hours before sample drawing. Venous blood samples of all patients will be drawn after admission in a fasting state. Routine blood specimens will be shipped to our

central clinical laboratory to be measured uniformly in a highly standardized center. Blood samples, including CBC, Matrix Gla protein, and INR will be assessed at every visit.

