## 8. STUDY ASSESSMENTS AND PROCEDURES

### 8.1 Standard Safety Laboratory Panel

Hematology

- Hemoglobin
- Hematocrit
- Red blood cell count
- White blood cell count and differential
- Platelet count

Serum chemistry

- Aspartate Aminotransferase (AST, SGOT)
- Alanine Aminotransferase (ALT, SGPT)
- Alkaline Phosphatase (reflex to GGTP)
- Creatine Kinase (Creatine Phosphokinase) (CK) (CPK) (reflex to troponin)
- Total Bilirubin
- Uric Acid
- Blood Urea Nitrogen (BUN)
- Electrolytes - sodium, potassium, chloride, Total Protein, Albumin
- Serum Creatinine (Scr)

EGFR will be estimated by the method of **Cockcroft-Gault**:

Cockcroft-Gault CrCl =  $(140 - \text{age}) * (\text{Wt in kg}) * (0.85 \text{ if female}) / (72 * \text{Cr})$

The eGFR is expressed in mL/min/1.73m^2

- Females only: urine HCG pregnancy test (HCG minimum sensitivity of 25 IU/L). If a urine HCG test is positive, patient will be excluded

Data to be Collected: Routine demographic and cardiovascular clinical data have been collected for all patients in the study. For CAC, we will collect Agatston and Volume scores, number of lesions and density for each plaque. For CCTA-specific variables, we will quantify and characterize the following APCs by both manual and automated plaque characterization methods:

- Coronary artery plaque volume
- Non-calcified plaque volume
- Calcified plaque volume
- Plaque location
- Plaque length
- Plaque distribution
- Arterial remodeling
- Low attenuation plaque (Hounsfield unit density <30 HU)
- Spotty calcifications

*2b1a. Overview:* In a single session at baseline and followup, after phlebotomy and physical examination, each subject will receive sequential non-contrast followed by contrast scans. The entire scanning procedure will take approximately 30 minutes.

*Screening.* Subjects will be screened for contraindications for beta-blockers and nitroglycerin (PDE5 inhibitors). The desired heart rate for adequate image quality is  $\leq 70$  bpm. If the heart rate is above this level, a beta-blocker will be prescribed. If a beta blocker is contraindicated, a calcium channel blocker will be given instead.

*2b1b. Noncontrast scan:* This will be performed to measure CAC. Patients will be positioned within the scanner with ECG leads, and a rhythm strip will be viewed. After a scout film is obtained, standard calcium scoring imaging will be performed at the end of inspiration.

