## **Procedures for Reporting Adverse Events (AE), Serious Adverse Events (SAE), Pregnancy, and Product Quality Complaints (PQC) to Janssen Scientific Affairs**

### **A. AEs, SAEs, Special Situations and Pregnancy Reporting.**

The Institution and the Sponsor Investigator will transmit SAEs and Special Situations in a form provided by Janssen Scientific Affairs in accordance with Section VIII Transmission methods, in English within 24-hours of becoming aware of the event(s).

All available clinical information relevant to the evaluation of a related SAE or Special Situation is required.

- The Institution and/or Sponsor Investigator are responsible for ensuring that these cases are complete and if not are promptly followed-up. A safety report is not considered complete until all clinical details needed to interpret the case are received. Reporting of follow-up information should follow the same timeline as initial reports.
- Copies of any and all relevant correspondences with regulatory authorities and ethics committees regarding any and all serious adverse events, irrespective of association with the Janssen Product under study, are to be provided to Janssen Scientific Affairs using a transmission method in Section VIII within 24 hours of such report or correspondence being sent to applicable health authorities.

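### The severe neutropenia example among the events of special interest puts its cut-off on total white cells instead of neutrophils, so the printed number can miss severely neutropenic patients

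*Combined protocol and SAP*

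**What the plan says.** Section 10, I.b (Adverse Events of Special Interest) explains why its list exists: "Events that Janssen Scientific Affairs is actively monitoring as a result of a previously identified signal (even if non-serious"). It then sets the reporting consequence: "The following are considered as events of special interest, and should be reported as a serious AE".

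The first bullet opens with "Suspected severe toxic effect on the bone marrow, such as severe thrombocytopenia (platelet count less than 50,000" per µL) and continues with "severe neutropenia (white blood cell count less than 500" per µL), followed by pancytopenia and aplastic anemia. No other section gives a neutrophil cut-off or corrects this one.

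The data needed for a neutrophil count are in the plan. The standard safety panel in section 8.1 includes "White blood cell count and differential". On timing, the text under Laboratory Measurements states "Blood samples, including CBC, Matrix Gla protein, and INR will be assessed at every visit", although that heading lists only 0, 6 and 12 months, and Figure 2 shows routine blood tests only on day 1 and at 6 and 12 months.

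Serious events go to the drug supplier "in English within 24-hours of becoming aware of the event(s") under the reporting procedures that follow section 11.

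**The concern.** Neutropenia is a low neutrophil count, and neutrophils are only one part of the total white count. The thrombocytopenia example in the same bullet is defined on its own cell line, platelets. The neutropenia example is the only numeric one there that names one cell type and measures another.

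What is at stake is the reporting route. The list is meant to bring in events even when they are not otherwise serious. An isolated low neutrophil count in an outpatient may meet none of the seriousness criteria in section 10, I.e except the judgement-based one for medically important events. A site that relies on the printed number might then record it as a non-serious event. It would fall outside the 24-hour transmission and the quarterly listing of serious events used for reconciliation.

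**Working it through.** The plan has no calculated figure to reproduce here, because the 500/µL is a definition. The check asks which patients the printed definition can reach.

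**Inputs from the documents.** The cut-off is a total white count below 500/µL (section 10, I.b). Enrolment is 110 (Study Design, item a) or 120 (synopsis, and the text after the secondary endpoints), allocated 1:1.

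**Inputs assumed.** The documents give no counts for white cells other than neutrophils, so these are varied. For illustration, neutrophil counts among affected patients are taken as uniform between 0 and 500/µL, and the figure of 500 is read on neutrophils for comparison.

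**Step 1, the identity.** Let N be the neutrophil count and L the count of all other white cells, per µL. Then:

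total white count = N + L

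A total below 500 implies N below 500, so the printed number does not flag patients above 500 neutrophils. The converse fails. A patient with N below 500 meets the printed number only if N < 500 − L.

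**Step 2, the bound.** If L ≥ 500, then 500 − L ≤ 0 and no value of N satisfies the condition, including N = 0. This needs no distributional assumption.

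**Step 3, a single patient.** A total of 2,000/µL with 20% neutrophils gives 2,000 × 0.20 = 400 neutrophils/µL. Neutrophils are below 500, yet the total is 2,000 / 500 = 4 times the printed cut-off.

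**Step 4, the share reached.** With N uniform on 0 to 500, the share of cases with N < 500 that meet the printed number is max(0, (500 − L) / 500).

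| Other white cells L (per µL, assumed) | Calculation | Share meeting the printed number |
|---|---|---|
| 0 | 500/500 | 100% |
| 100 | 400/500 | 80% |
| 250 | 250/500 | 50% |
| 400 | 100/500 | 20% |
| 500 or more | 0 | 0% |

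Letting L vary between patients gives the same pattern. With L lognormal and a log-scale standard deviation of 0.3 to 0.7, simulation gives a share of 10% to 19% at a median of 500/µL, 1.1% to 8.9% at 750/µL, and 0.1% to 4.5% at 1,000/µL. These medians are assumptions too.

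**Step 5, patients exposed.** Reporting to the supplier concerns its own product, so the relevant group is the rivaroxaban arm: 110 / 2 = 55 or 120 / 2 = 60.

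**The case against.** The strongest reply is that the number is an illustration. The reportable event is a suspected severe toxic effect on the marrow, and the cytopenias are introduced as examples. An investigator who sees 400 neutrophils/µL can report it on suspicion, whatever the parenthesis says. This stands, and it limits the claim to what a site might fail to do.

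Other routes also stand. Section 10, I.e makes medically important events serious on judgement, and hospitalisation or a life-threatening course qualifies as well. Section 11 has every adverse event recorded, serious or not, and Maintenance of Safety Information has all of them supplied in report format. A summary of events of special interest can also be requested for reconciliation. The data are therefore not lost. What could be lost is the 24-hour timing, and a place in the routine quarterly listing, for a case that nobody judged to be suspected marrow toxicity or medically important.

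Three stronger readings are tempting and are not supported:

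- A reader might infer that nearly all real cases would miss the cut-off. That depends on how far the other white cells are depleted in affected patients. The documents do not say, and the table runs from 100% to 0%.
- A reader might infer that reporting is compulsory and hinges on the number. The plan says these events should be reported, and the number is not a strict gate.
- A reader might infer that a total below 500/µL merely repeats pancytopenia, listed in the same bullet. A low white count alone says nothing about red cells or platelets.

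None of this removes the mismatch. A numeric example helps a site to recognise a case without relying on judgement alone, and one attached to the wrong quantity invites a missed report.

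**Conclusion.** The concern holds as an error in a safety-reporting definition. The label and the measured quantity disagree, and nothing elsewhere in the documents corrects this. That the printed number cannot be met once other white cells reach 500/µL is arithmetic and rests on no assumption. The partial shares below that level depend on the assumed counts and on the uniform distribution for neutrophils.

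The practical size is small. It concerns about 55 to 60 patients on rivaroxaban, and the risk lists in section 9 do not name neutropenia. The likely harm is a delayed report of an individual case. Sample size, power and every efficacy result are unaffected. The documents show that term and measure disagree, but they do not contain the supplier's source text, so they cannot settle what cut-off was intended.

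**What to change.** In section 10, I.b, and in the instructions for the serious adverse event form, express the neutropenia example as an absolute neutrophil count, so that the term and the measured quantity agree. Derive the count from the total white count and differential in the section 8.1 panel. Reconcile the cut-off with the drug supplier's safety-reporting source text before the wording is final; no value is proposed here.

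The cost is one phrase in the protocol, a matching line in the form instructions, and the supplier's agreement. No new sample, assay or visit is needed.

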**c. Individual Case Safety Report (ICSR)**

A valid ICSR must contain the four minimum criteria required to meet regulatory reporting requirements.

- an identifiable subject (not disclosing the subject's name and address)
- an identifiable reporter (investigational site)
- a Janssen medicinal product
- an adverse event, outcome, or certain special situation

The minimum information required is:

- suspected Janssen product (doses, indication)
- date of therapy (start and end date, if available)
- batch or lot number, if available
- subject details (subject ID and country)
- gender
- age at AE onset
- reporter ID
- adverse event detail (AE verbatim in English), onset date, relatedness, causality, action taken, outcome, (if available)
- Janssen protocol ID

**d. Product Quality Complaint (PQC)**

A product quality compliant is related to a potential quality issue during manufacturing, packaging, release testing, stability monitoring, dose preparation, storage or distribution of the product, or delivery system. Not all PQCs involve a subject. Lot and batch numbers are of high significance and need to be collected whenever available.

Examples of PQC include but not limited to:

- Functional Problem: e.g., altered delivery rate in a controlled release product
- Physical Defect: e.g. abnormal odor, broken or crushed tablets/capsules
- Potential Dosing Device Malfunction: e.g., autoinjector button not working, needle detaching from syringe

- Suspected Contamination
- Suspected Counterfeit.

**e. Serious Adverse Event (SAE)**

A serious adverse event based on ICH and EU Guidelines on Pharmacovigilance for Medicinal Products for Human Use is any untoward medical occurrence that at any dose:

- Results in death
- Is life-threatening  
(The subject was at risk of death at the time of the event. It does not refer to an event that hypothetically might have caused death if it were more severe.)
- Requires inpatient hospitalization or prolongation of existing hospitalization
- Results in persistent or significant disability/incapacity
- Is a congenital anomaly/birth defect
- Is a suspected transmission of any infectious agent via a medicinal product
- Is medically important\*

\*Medical and scientific judgment should be exercised in deciding whether expedited reporting is also appropriate in other situations, such as important medical events that may not be immediately life threatening or result in death or hospitalization but may jeopardize the subject or may require intervention to prevent one of the other outcomes listed in the definition above. These should usually be considered serious.

**NOTE: DEATH FOR ANY REASON SHOULD BE REPORTED AS A SERIOUS ADVERSE EVENT.**

For reports of hospitalization, it is the sign, symptom or diagnosis which led to the hospitalization that is the serious event for which details must be provided.

Any event requiring in-patient hospital admission (or the prolongation of hospitalization) must be reported as an SAE. Events that do not meet the criteria for SAE reporting are:

- Reasons described in the Protocol, e.g. drug administration, Protocol-required testing
- Social reasons, e.g. overnight stay because of distance between home and hospital
- Surgery or procedure planned and documented prior to entry into the Study.

Any event requiring hospitalization or prolongation of hospitalization that occurs during the study must be reported as a serious adverse event, except hospitalizations for the following:

- Hospitalizations not intended to treat an acute illness or adverse event (e.g., social reasons such as pending placement in long-term care facility)
- Surgery or procedure planned before entry into the study. [Note: Hospitalizations that were planned before the start of data collection and where the underlying condition for which the hospitalization was planned has not worsened will not be

considered serious adverse events. Any adverse event that results in a prolongation of the originally planned hospitalization is to be reported as a new serious adverse event.]

The cause of death of a subject in a study within 30 days of the last dose of study drug, whether or not the event is expected or associated with the study drug, is considered a serious adverse event.

**f. Unlisted (Unexpected) Adverse Event/Reference Safety Information**

An adverse event is considered unlisted if the nature or severity is not consistent with the applicable product reference safety information. For a medicinal product(s) with a marketing authorization, the expectedness of an adverse event will be determined by whether or not it is listed in the applicable product information.

**II. Special Situations**

Safety events of interest for a Janssen medicinal product that require expediting reporting and/or safety evaluation include, but are not limited to:

- Drug exposure during pregnancy (maternal and paternal)
- Overdose of a Janssen medicinal product
- Exposure to a Janssen medicinal product from breastfeeding
- Suspected abuse/misuse of a Janssen medicinal product
- Inadvertent or accidental exposure to a Janssen medicinal product
- Any failure of expected pharmacological action (i.e., lack of effect) of a Janssen medicinal product
- Medication error involving a Janssen medicinal product (with or without patient exposure to the Janssen medicinal product, e.g., name confusion)
- Suspected transmission of any infectious agent via a medicinal
- Unexpected therapeutic or clinical benefit from use of a Janssen medicinal product

These safety events may not meet the definition of an adverse event; however, they are treated in the same manner as adverse events. Special situations should be recorded on the Adverse Event page of the CRF.

Any special situation that meets the criteria of a serious adverse event should be recorded on a Serious Adverse Event Report Form and be reported to Janssen Scientific Affairs **within 24 hours of becoming aware of the event.**

**III. Pregnancy**

All initial reports of pregnancy must be reported to Janssen Scientific Affairs by the Sponsor Investigator **within 24 hours of their awareness of the event** using the Serious Adverse Event Form. Abnormal pregnancy outcomes (e.g. spontaneous abortion, stillbirth, and congenital anomaly) are considered serious adverse events and must be reported using the Serious Adverse Event Form.

Any subject who becomes pregnant during the study must be promptly withdrawn from the study and discontinue further study treatment.

Because the effect of the Janssen medicinal product on sperm is unknown, pregnancies in partners of male subjects exposed to a Janssen medicinal product will be reported by the Sponsor Investigator **within 24 hours of their awareness of the event** using the Serious Adverse Event Form. Depending on local legislation this may require prior consent of the partner.

Follow-up information regarding the outcome of the pregnancy and any postnatal sequelae in the infant will be required.

## **11. Reporting Procedures for Adverse Events and Pregnancies [and/or Pregnancies in Partners]**

All adverse events, whether serious or non-serious, related or not related, special situations, pregnancy exposures and/or pregnancies in partners following exposure to a Janssen medicinal product are to be documented by the investigator and recorded in the CRF and in the subject's source records. Investigators must record in the CRF their opinion concerning the relationship of the adverse event to a Janssen medicinal product.

All (serious and non-serious) adverse events reported for a Janssen medicinal product should be followed-up in accordance with clinical practice.

All serious adverse events that have not resolved by the end of the study, or that have not resolved upon discontinuation of the subject's participation in the study, must be followed until any of the following occurs:

- The event resolves
- The event stabilizes
- The event returns to baseline, if a baseline value/status is available
- The event can be attributed to agents other than the study drug or to factors unrelated to study conduct
- It becomes unlikely that any additional information can be obtained (subject or health care practitioner refusal to provide additional information, lost to follow-up after demonstration of due diligence with follow-up efforts)

All serious adverse events, pregnancy exposures and/or pregnancies in partners for Janssen medicinal products under study should be reported directly by the Sponsor Investigator, **within 24 hours of becoming aware**, to Janssen Scientific Affairs using the Janssen Scientific Affairs Serious Adverse Event Report Form. In the event the study is blinded, the Sponsor Investigator will submit an unblinded SAE or pregnancy exposure report to Janssen Scientific Affairs.

All follow-up information for serious adverse events that are not resolved at the end of the study or by the time of patient withdrawal must be reported directly by the Sponsor Investigator, within 24 hours becoming aware, to Janssen Scientific Affairs using the Janssen Scientific Affair's Serious Adverse Event Report Form.

